7.10.3.2 ROC Analysis

In this pilot study we are assuming that any fluorescence is indicative of tumor presence. To assess how the amount of observed fluorescence (e.g., the SBR or TBR) may affect the diagnostic accuracy of pegasitacianine, a receiver operating characteristic (ROC) analysis will be performed on all specimens using the observed thresholds of SBR and TBR. The corresponding ROC curve will be provided along with the area under the curve (AUC).

7.10.3.3 Adjustment for Clustering

There is potential for within-subject correlation to bias our estimates of pegasitacianine's diagnostic accuracy. To assess this issue, an ROC curve will be constructed from a mixed model that clusters specimens by the subject they originated from. We will compare the AUC of the mixed effects ROC curve to the standard ROC curve to assess if within-subject correlation is causing significant bias in our analyses. If it is determined that significant bias has been introduced, additional analyses on secondary endpoints may be performed to assess the diagnostic accuracy of pegasitacianine.

The confidence intervals for diagnostic accuracy (e.g. the positive predictive value, negative predictive value, sensitivity, specificity, and true/false negative/positive rate) will also be constructed via a cluster-bootstrap to determine confidence intervals that account for the effects of within-subject clustering. Since the number of specimens each subject has is variable, in order to keep the same number of specimens in the bootstrapped sample, we will cluster initially by the number of specimens each subjects has, and then resampling will occur by first choosing a subject within that cluster and then resampling the same number of specimens they originally had.

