7.2 Reporting Conventions

The following conventions will be applied to all data presentations and analyses:

- Continuous variables will generally be summarized by the number of patients with missing and non-missing values, mean, standard deviation, median, Q1 (quartile 1), Q3 (quartile 3), minimum, and maximum.
- Categorical variables will be summarized by the number and percentage of patients within each category. If not specified otherwise, the number of patients with non-missing values will be the denominator for percentage calculations. The number of patients with missing values will be presented.
- Confidence intervals will be reported as two sided at the 95% level.
- All mean and median values will be formatted to one more decimal place than the measured value.
- Standard deviation values will be formatted to two more decimal places than the measured value.
- Minimum and maximum values will be presented with the same number of decimal places as the measured value.
- For non-efficacy values the number and percent of responses will be presented in the form XX (XX %), where the percentage is in parentheses. Percentages will be rounded to

the nearest percent. In the case of a frequency of zero, the frequency and percentage will be presented as 0 rather than 0 (0%).

- Date variables will be formatted as DDMMYY for presentation

All the analyses will be run displaying Group (Group 1 vs. Group 2). All rates will be summarized using counts and percentages.

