7.10.2 Secondary Analyses

7.10.2.1 Analysis of Diagnostic Imaging

The positive predictive value, negative predictive value, sensitivity, and specificity (biopsy level) will be calculated and summarized for each Group. The summary will include the true/false negatives/positive rate and number of specimens. Two-sided 95% confidence intervals will be calculated for each rate via Clopper-Pearson method.

A listing by subject and specimen showing the fluorescence status, pathology result, specimen type (SOC vs. fluorescence), suspicious vs. normal, fluorescence in *in situ* and *ex situ*, and fluorescence measures (MFI, SBR or TBR) will be provided.

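### The cluster bootstrap in SAP 7.10.3.3 does not reliably account for clustering: its intervals can be too narrow where few patients share a specimen count and too wide where many do and the correlation is low

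*SAP*

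**What the plan says.** The main intervals for the four diagnostic measures ignore clustering. SAP 7.10.2.1 states: "Two-sided 95% confidence intervals will be calculated for each rate via Clopper-Pearson method". SAP 7.10.3.3, under Exploratory Analyses, adds a second set by cluster bootstrap, "to determine confidence intervals that account for the effects of within-subject clustering". The scheme has two stages:

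- **Stage 1.** "we will cluster initially by the number of specimens each subjects has, and then resampling will occur by first choosing a subject within that cluster". The reason given is "in order to keep the same number of specimens in the bootstrapped sample".
- **Stage 2.** "then resampling the same number of specimens they originally had".

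The section does not say whether stage 2 is with replacement, what happens when only one patient has a given count, how many draws are made, or which type of bootstrap interval is used. SAP 7.2 displays all analyses by Group, so I assume that the strata are formed within a Group.

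**The concern.** A cluster bootstrap captures patient-to-patient variation by letting patients replace one another. Here a patient can be replaced only by someone with exactly the same number of specimens. A patient whose count is unique is drawn every time, and that stratum then contributes no between-patient variance. Stage 2 works the other way: the variation of patient means already contains the within-patient noise, and resampling specimens adds it again.

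The stated reason does not require this. By the formulas in SAP 5.1.2, the denominators are tumour, non-tumour, fluorescent or non-fluorescent specimens. Fixing the total number of specimens fixes none of these.

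These are the plan's only clustering-aware intervals for the secondary endpoints. SAP section 4 says that the study is meant to inform power calculations for later trials, so interval width is one of its main products. SAP section 1 gives the SAP precedence over the protocol on analysis, so this wording is what will be programmed.

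**Working it through.** The plan states no interval width, coverage or ICC, so there is no figure to reproduce.

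**Inputs from the documents.** Two-sided 95% intervals (SAP 7.2). About 60 patients in total (SAP section 4), with no set allocation between Groups (Protocol Summary, Sample Size). Up to 15 SOC specimens per patient, 10 suspected tumour and 5 normal (Protocol 6.3), plus fluorescence-guided specimens with no stated cap.

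**Inputs assumed.** ICC (rho) 0 to 0.4; sensitivity 0.85; specificity 0.70; specimen counts per patient either *mid* (uniform 8-15 plus Poisson 1.5), *wide* (uniform 3-15 plus Poisson 2) or *near the cap* (15 plus Poisson 1).

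**Step 1: algebra.** Take a stratum of m patients with n relevant specimens each, and let s2 = p(1-p).

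- True variance of the stratum proportion: s2[1+(n-1)rho]/(mn).
- Stage 1 reproduces (m-1)/m of it.
- Stage 2 adds s2(1-rho)(n-1)/(mn^2).

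Bootstrap variance / true variance = (m-1)/m + (1-rho)(n-1)/{n[1+(n-1)rho]}.

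With n = 10, the second term is:
- rho 0: 9/10 = 0.900
- rho 0.2: 0.8 x 9/(10 x 2.8) = 0.257
- rho 0.4: 0.6 x 9/(10 x 4.6) = 0.117

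SE ratios (square roots; 1.00 is correct):

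| rho | m = 1 | m = 2 | m = 50 |
|---|---|---|---|
| 0 | 0.95 | 1.18 | 1.37 |
| 0.2 | 0.51 | 0.87 | 1.11 |
| 0.4 | 0.34 | 0.79 | 1.05 |

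The errors cancel at about m = 4 for rho 0.2 (0.750 + 0.257 = 1.007) and about m = 8 for rho 0.4 (0.875 + 0.117 = 0.992). Direction is therefore set by the number of patients per stratum and by the ICC. If stage 2 is without replacement it does nothing: the second term vanishes and the ratio is below 1 for every m.

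**Step 2: simulation.** Beta-binomial data, 1000 datasets per cell, 400 draws, percentile intervals. Each cell gives SE ratio / coverage for sensitivity 0.85; the last column (Clopper-Pearson) gives coverage only.

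| Patients, counts | ICC | SAP, stage 2 with replacement | SAP, stage 2 without | Whole-patient bootstrap | Clopper-Pearson |
|---|---|---|---|---|---|
| 8, mid | 0.1 | 0.85 / 0.865 | 0.50 / 0.491 | 0.91 / 0.858 | 0.891 |
| 8, mid | 0.2 | 0.77 / 0.822 | 0.54 / 0.499 | 0.92 / 0.852 | 0.826 |
| 8, mid | 0.4 | 0.63 / 0.693 | 0.50 / 0.462 | 0.89 / 0.805 | 0.664 |
| 8, wide | 0.1 | 0.82 / 0.845 | 0.43 / 0.372 | 0.93 / 0.851 | 0.905 |
| 8, wide | 0.2 | 0.70 / 0.779 | 0.43 / 0.356 | 0.89 / 0.838 | 0.820 |
| 8, wide | 0.4 | 0.58 / 0.670 | 0.43 / 0.347 | 0.89 / 0.797 | 0.712 |
| 50, mid | 0.1 | 1.10 / 0.958 | 0.87 / 0.887 | 0.98 / 0.926 | 0.858 |
| 50, mid | 0.2 | 1.06 / 0.948 | 0.90 / 0.893 | 1.01 / 0.935 | 0.810 |
| 50, mid | 0.4 | 0.93 / 0.915 | 0.85 / 0.882 | 0.96 / 0.928 | 0.665 |

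At 8 patients, about 48% (mid) or 62% (wide) are alone in their stratum; at 50 patients (mid), 3%.

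Other cells:

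- **ICC 0, sensitivity.** At 50-60 patients the SE ratio is 1.31-1.36 with coverage about 0.99. At 8-10 patients with spread-out counts it is 1.09-1.10.
- **Counts near the cap, 10 patients, sensitivity.** 1.26, 1.04, 0.94 and 0.91 at ICC 0, 0.1, 0.2 and 0.4.
- **Specificity 0.70, 8 patients, all three count patterns.** 0.91-1.08, 0.83-1.01 and 0.71-0.89 at ICC 0.1, 0.2 and 0.4.
- **Specificity 0.70, 50 patients.** 1.11-1.18, 1.08-1.15 and 0.97-1.09 at the same ICCs.
- **Linearised patient-cluster logit-t interval.** Coverage 93-97%.

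**The case against.** A reader might infer that the intervals are always too narrow in a small Group and too wide in a large one. The documents do not support that. They give neither the ICC nor the specimen counts, and the sign of the error depends on both. Ten patients near the specimen cap give intervals that are too wide at ICC 0 (1.26). Fifty patients at ICC 0.4 give a ratio of 0.93 (mid counts), slightly narrow.

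The case for leaving the section alone has four further parts.

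- **Some of the small-Group shortfall is generic.** At 8 patients and ICC 0.1, a whole-patient percentile bootstrap covers no better (0.858 against 0.865 with mid counts). This stands. The scheme's own defect shows at ICC 0.2 and above, and it is why a plain bootstrap is not a sufficient remedy in a small Group.
- **The supplement helps in a large Group.** At 50 patients and ICC 0.2 it covers 0.948 against 0.810 for Clopper-Pearson. This stands. At 8 patients, however, it is no clear improvement on the unadjusted interval (0.822 against 0.826 with mid counts at ICC 0.2).
- **The widening depends on reading stage 2 as with replacement.** This is true, but the other reading leaves the intervals too narrow in every cell tabulated.
- **Nothing hangs on these intervals.** The section is exploratory, the primary analysis of clinically significant events is per patient, and there is no hypothesis test. Opening Group 2 rests on point values of 70% in Protocol 3.1 and on sponsor discretion in SAP 3.1. Group 2 may never open. All of this stands, and it limits the severity.

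**Conclusion.** The rule is wrong as written and should be fixed, but it is not critical. The mechanism follows from the algebra. The size does not follow from the documents and rests on the assumed ICC, counts and accuracy.

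- **Strata of one or two patients, material ICC.** At 8-10 patients with spread-out counts and ICC 0.1-0.4, the SE for a sensitivity of 85% is about 10-40% too small and coverage about 70-90%. For a specificity of 70% the shortfall is milder.
- **Large strata, low ICC.** At 50-60 patients and ICC 0-0.1, the SE is about 10-35% too large.
- **Large Groups at ICC 0.2-0.4.** Coverage is close to nominal.
- **Stage 2 without replacement.** Only the narrowing remains.

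Since a reader of the results cannot tell which case applies, the intervals cannot be taken as adjusted for clustering. Point estimates, the primary analysis and the Clopper-Pearson intervals are unaffected.

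**What to change.** Replace the last sentence of SAP 7.10.3.3 so that, within each Group, the patient is the only sampling unit. Two methods do this:

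1. **Whole-patient bootstrap.** Draw patients with replacement and keep all their specimens, with no strata by specimen count and no second-stage resampling. Let the specimen total vary. State the number of draws and the interval type.
2. **Linearised interval.** For k patients with y_i successes among n_i relevant specimens, let p = sum(y_i)/sum(n_i) and v = [k/(k-1)] x sum[(y_i - p n_i)^2] / [sum(n_i)]^2. The interval is logit(p) +/- t(k-1, 0.975) x sqrt(v)/[p(1-p)], transformed back.

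Use method 2 when a Group has about 15 patients or fewer, because the whole-patient bootstrap covered only about 83-90% at around 10 patients. Name a fallback for estimates of 0% or 100%, where the logit interval is undefined and the bootstrap collapses to a point. Clopper-Pearson on an effective sample size is one option; the rule for that size must be written down, because such data carry no information on the ICC.

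The cost is a few lines of SAP text and simpler code, and SAP 7.1 allows updates before database lock. Some intervals will become wider and others narrower.

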7.10.3.4 Camera System Analysis

An analysis on diagnostic results by camera system will be performed. 2x2 incidence tables comparing the true/false negative/positive results will be constructed for each camera system, and compared via the Breslow-Day test to assess if there is any effect of camera system on diagnostic results (e.g. to test if the common odds-ratio of each incidence table is equivalent across camera types). A summary including the diagnostic true/false negative/positive numbers and rates for each camera system, sensitivity, specificity, and p-value of this analysis will be provided.

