Indications	Pegsitacianine is indicated as an imaging agent for intraoperative detection of peritoneal metastases originating from intra-abdominal tumors such as ovarian, colorectal, and gastric cancers. Pegsitacianine is administered intravenously as a single dose prior to surgery.
Study Centers	up to 10 centers
Trial Objectives	
Primary Objective:
 
The primary objective of this study is to determine if administration of pegsitacianine (mg/kg) results in the detection of metastatic disease left behind following standard of care surgical resection of peritoneal metastases.
 
Secondary Objectives:
 
Key secondary objectives are to demonstrate an acceptable safety profile, reliable sensitivity, specificity, negative predictive values, and positive predictive values of the imaging agent at the level of the individual specimens.

Background	Pegsitacianine is an intraoperative nanoparticle-based fluorescence imaging agent that was evaluated in the first-in-human Phase 1 study (ON-1001) completed in the Netherlands in patients with solid cancers undergoing surgical excision of their tumors. In addition, it was also evaluated in the completed Phase 2 study (ON-1002) in solid tumors. Pegsitacianine fluorescence is quenched when exposed to normal physiological pH but becomes activated following micellar disassembly in the low-pH tumor microenvironment. Pegsitacianine was demonstrated to be well tolerated and showed no dose-limiting toxicity (DLT).

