2. STUDY OBJECTIVES

2.1 Objectives and Endpoints

The main objective of this study is to investigate whether pegsitarcianine can detect residual disease in the peritoneal cavity following standard of care (SOC) resection of peritoneal metastases using a [REDACTED] mg/kg dose administered [REDACTED] prior to surgery.

Table 1. Objectives and Endpoints

Objectives	Endpoints
Primary Objective	Primary Endpoint

The primary objective of this study is to determine if administration of pegasitacianine (█ mg/kg) results in the detection of metastatic disease left behind following standard of care surgical resection of peritoneal metastases.
	
Rate of detection of disease left behind following SOC resection of peritoneal metastases as measured by rate of Clinically Significant Events (CSEs).

Secondary Objectives	Secondary Endpoints

Demonstrate reliable sensitivity, specificity, negative predictive values (NPPV), and positive predictive values (PPV) of the imaging agent at the level of the individual specimens.
	
Sensitivity, specificity, negative predictive values (NPV), and positive predictive values (PPV).

Demonstrate an acceptable safety profile.	Incidence of TEAEs and SAEs, abnormalities in lab values, vital signs, or ECG results.
Exploratory Objectives	Exploratory Endpoints
Assess the how the normalized SBR value affects the diagnostic accuracy of pegsitacianine in detection of metastatic disease vs. normal tissue.	ROC analysis across various specimen-to-background ratio fluorescence thresholds.
Effect of camera system on diagnostic results.	Diagnostic results across various camera systems.
Assess amount of fluorescence shown in various types of specimens.	Mean fluorescence intensity and Specimen-to-background ratio

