7.5 Adjustment for Multiplicity

There are no planned adjustments for multiple endpoints or analyses.

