7.6 Adjustment for Multiple Centers

Differences between study centers will not be incorporated into the statistical analyses for this study. There are no plans to analyze data within centers.

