7.9.5 Cytoreductive Surgery Details and Specimen Collection

Cytoreductive surgery details including the following will be summarized on a patient level using descriptive statistics in the Safety population:

- Duration of surgery
- Suspected PCI score and fluorescence imaging PCI score
- Method of localization

- Number of SOC suspicious nodules collected
- Number of SOC normal specimens collected
- Additional fluorescent areas collected
- Cytoreduction score
- Time spent imaging
- Camera system used

A listing will also be generated.

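### The camera-system test is offered as a test of any camera effect, but it tests only whether the odds ratio is equal across cameras

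*SAP*

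**What the plan says.** SAP 2.1, Table 1, lists an exploratory objective: "Effect of camera system on diagnostic results". SAP 7.10.3.4 serves it with one 2x2 table per camera system, "compared via the Breslow-Day test to assess if there is any effect of camera system on diagnostic results". The same sentence explains the test in a parenthesis: "to test if the common odds-ratio of each incidence table is equivalent across camera types". The planned output is counts and rates of true and false positives and negatives, sensitivity and specificity for each camera, and one p-value. The section lists no interval for the camera-specific values and no difference between cameras.

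Four other places bear on this:

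- SAP 7.10.3.3 acknowledges within-patient correlation and has the accuracy intervals "constructed via a cluster-bootstrap to determine confidence intervals that account for the effects of within-subject clustering". It does not extend this to the camera test.
- SAP 7.6 says: "Differences between study centers will not be incorporated into the statistical analyses for this study". The Protocol Summary gives "up to 10 centers".
- SAP 7.5 says: "There are no planned adjustments for multiple endpoints or analyses".
- SAP 5.1.2 pools SOC and pegsitacianine-guided specimens when it defines the accuracy measures.

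**The concern.** The stated aim and the hypothesis tested are different. The study's diagnostic endpoints are sensitivity, specificity, PPV and NPV; the odds ratio is not one of them. A camera can change sensitivity and specificity a great deal and leave the odds ratio alone. That pattern is plausible here, because a specimen counts as positive on any fluorescence: a camera that picks up more signal could call more tumor and more normal tissue fluorescent.

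The risk is that a non-significant p-value, presented as a test of any effect, is read as evidence that the camera does not matter. The study is meant to inform the design of later ones, so that reading could carry forward.

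**Working it through.** **No plan figure to reproduce.** The documents give no alpha, number of cameras, effect size or power for this test. I take alpha as 0.05, in line with the 95% interval convention in SAP 7.2.

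**The algebra.** Diagnostic odds ratio = [Se/(1−Se)] × [Sp/(1−Sp)].

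- 90/50: (0.9/0.1) × (0.5/0.5) = 9.
- 50/90: (0.5/0.5) × (0.9/0.1) = 9.

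**A worked table.** Take 30 patients per camera, with 10 tumor and 5 non-tumor specimens each (assumed, from the cap of 10 suspected tumor and 5 normal specimens in Protocol 6.3). That gives 300 tumor and 150 non-tumor specimens per camera. At expected counts:

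- Camera at 70/90: 210 true positives, 90 false negatives, 135 true negatives, 15 false positives. Odds ratio = (210 × 135)/(90 × 15) = 21.
- Camera at 90/70: 270, 30, 105 and 45. Odds ratio = (270 × 105)/(30 × 45) = 21.

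The Breslow-Day statistic is 0.0 (p = 1.0). The direct chi-square for sensitivity is 0.2²/(0.8 × 0.2 × 2/300) = 37.5. For specificity it is 0.2²/(0.8 × 0.2 × 2/150) = 18.75.

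**Rejection rates.** Assumptions, none from the documents: 50 evaluable patients, 25 per camera, one camera per patient, 10 + 5 specimens. Rates below are for independent specimens (6,000 runs).

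| Sensitivity/specificity | Odds ratios | Breslow-Day rejects |
|---|---|---|
| 90/50 vs 50/90 | 9.0 vs 9.0 | 5.1% |
| 85/60 vs 70/78.5 | 8.50 vs 8.52 | 4.9% |
| 90/60 vs 80/85 | 13.5 vs 22.7 | 26% |
| 95/60 vs 80/95 | 28.5 vs 76 | 45% |

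For the first two pairs, separate patient-clustered 95% intervals for the sensitivity and specificity differences show at least one exclusion of 0 in over 99% of runs. With 30 patients per camera and 10,000 runs, Breslow-Day rejects 5.2% for identical cameras at 80/80, 5.2% for 80/80 vs 90/64, and 5.3% for 70/90 vs 90/70.

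**Clustering.** Let patients differ in how readily their tissue fluoresces, with latent intraclass correlation (ICC) 0.1, 0.2 or 0.3. Let rho be the correlation between the patient effect on tumor and on non-tumor specimens. For identical cameras (85/70, 25 patients each), Breslow-Day rejects:

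| rho | ICC 0.1 | ICC 0.2 | ICC 0.3 |
|---|---|---|---|
| 0 | 9% | 13% | 17% |
| 0.5 | 7% | 9% | 11% |
| 1 | 5% | 5% | 5% |

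At rho = 1 a patient's tendency to fluoresce raises sensitivity and lowers specificity together, so it largely cancels in the odds ratio. At ICC 0.2 the equal-odds-ratio pairs are rejected in about 12%, 9% and 5% of runs (rho 0, 0.5, 1), about the same as identical cameras. The p-value therefore carries almost no information on this kind of difference. The separate clustered intervals still show the two pairs in 100% and 90-95% of runs.

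**Guided specimens.** Protocol 3.1 and 6.3 have these excised because they fluoresce, so nearly all are true or false positives. Assume identical cameras with 70% specificity on 5 SOC non-tumor specimens, and guided specimens that are all positive ex situ and 60% tumor, averaging 3 per patient with one camera and 1 with the other. Pooled specificity is then 3.5/(5 + 3 × 0.4) = 56.5% against 3.5/(5 + 1 × 0.4) = 64.8%. That is a false gap of about 8 points. At least one clustered interval excludes 0 in 28-36% of runs, against 10-14% for Breslow-Day. Any direct comparison by camera must therefore keep guided specimens apart.

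**The case against.** Much of the case on the other side stands. The SAP does not conceal the limit: its parenthesis names the odds ratio. A large trade-off would be plain from the tabulated sensitivity and specificity. SAP 7.10.2.1 lists fluorescence and pathology by specimen, and camera is recorded in a section where "Cytoreductive surgery details including the following will be summarized on a patient level". SAP 7.10.3.5 allows post-hoc evaluation of sensitivity and specificity against other covariates. The objective is exploratory, and SAP section 4 says the study is not formally powered for testing. What remains is that the only inferential output is a p-value with too broad a label, and that no planned interval or difference helps a reader judge what the table shows.

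Three stronger readings are tempting, and the documents do not support them:

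- *The test is blind to camera effects in general.* It is not. Besides the 26% and 45% above, with 30 patients per camera it rejects 57.6% for 80/80 vs 90/80 and 97.7% for 80/80 vs 90/90. The blind spot is confined to near-equal odds ratios, and nothing in the documents says how likely those are.
- *The p-value is certainly too liberal.* That depends on rho and the ICC, and neither is given.
- *Camera is confounded with center.* The documents do not say how cameras are distributed over centers. If each center uses one camera, no test could separate the two, which is a limit of the data and not a fault of Breslow-Day. SAP 7.6 also leaves center out by deliberate choice, so a center-stratified analysis is not called for on this evidence.

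**Conclusion.** The point holds and is minor. The wording claims more than the test can deliver: for cameras that trade sensitivity against specificity at about the same odds ratio, Breslow-Day rejects only at its null rate. That rate is about 5% with independent specimens. At an assumed ICC of 0.2 it is about 12-13% if tumor and non-tumor patient effects are uncorrelated, and about 5% if they are fully correlated.

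The algebra needs no assumption. The rates rest on the assumed number of cameras, patient split, specimen counts, accuracy values and correlations. A reader might infer that the study's diagnostic results are in doubt. They are not: the effect is limited to one exploratory objective, and no primary or secondary endpoint or planned decision uses this p-value.

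**What to change.** 1. In SAP 7.10.3.4, describe the test as one of *homogeneity of the diagnostic odds ratio across camera systems*, and state that its p-value is unadjusted for clustering and center.
2. Make estimates the main output: sensitivity and specificity per camera, and their between-camera differences, with patient-clustered 95% confidence intervals (GEE clustered by patient, or a patient-level cluster bootstrap). Compute them on SOC specimens, suspicious and normal. Show pegsitacianine-guided specimens separately, as number per patient and PPV by camera.
3. Tabulate camera by center, and add one caveat that camera and center effects cannot be separated if each center uses a single camera.

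The cost is SAP wording and analysis code; no new data are needed. There are four downsides:

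- Two unadjusted comparisons replace one. With two identical cameras and a 25/25 split, at least one interval excludes 0 in about 9-10% of trials (1 − 0.95² = 9.75% if the two were independent). Leaving this unadjusted agrees with SAP 7.5, but it should be stated.
- Precision is modest. At 25/25 with ICC 0.2, the median half-width is 8.8 points for the sensitivity difference and 14.4 points for the specificity difference.
- Applied within camera, the SAP 7.10.3.3 bootstrap is less reliable when a camera has few patients (simulated coverage 0.890-0.967 at a 40/10 split).
- The camera table will not add up to the pooled accuracy table in SAP 7.10.2.1, because guided specimens are shown apart. A footnote should say so.

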6.5 Training

Extensive training will be provided to all study staff. Initial training will occur at the Site Initiation Visit, followed by on-site training that will take place during the initial surgical procedures with Sponsor Representatives present in the operating room during the procedures. Sponsor Representatives will ensure all study personnel are adequately trained and follow identical procedures to preserve the integrity of the collected data without providing input on the selection of specimens or their fluorescent status, these tasks are the sole responsibility of the operating surgeon. Additional retraining may take place if necessary throughout the course of the study. Training will include a review of protocol procedures, NIR camera operating instructions, documentation of specimens and their fluorescence status, and upload of source documentation. All training will be documented and stored within the Trial Master File.

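### The camera-system test takes no account of center, so if cameras are wholly or partly tied to centers, a center or surgeon difference in the diagnostic odds ratio can be reported as a camera effect

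*SAP*

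**What the plan says.** SAP 2.1, Table 1, lists "Effect of camera system on diagnostic results" among the exploratory objectives. SAP 7.10.3.4 carries it out with one table of true and false positives and negatives per camera. The tables are to be "compared via the Breslow-Day test to assess if there is any effect of camera system on diagnostic results", which the SAP explains as "to test if the common odds-ratio of each incidence table is equivalent across camera types". The output is the true/false positive/negative numbers and "rates for each camera system, sensitivity, specificity, and p-value of this analysis will be provided". No center, surgeon or patient term appears in that section.

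SAP 7.6 states: "Differences between study centers will not be incorporated into the statistical analyses for this study". It adds: "There are no plans to analyze data within centers".

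Four other places bear on the point:

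- The Protocol Summary allows "up to 10 centers".
- Protocol 6.5 says of specimen selection and fluorescence status that "these tasks are the sole responsibility of the operating surgeon".
- Protocol 5.3 marks randomization as not applicable.
- SAP 7.9.5 summarizes the camera used at patient level, but neither document gives a rule for assigning cameras to patients or sites.

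**The concern.** Each specimen's place in the 2x2 table depends on which tissue the surgeon samples and whether the surgeon calls it fluorescent. Surgeons belong to centers. If a center works mainly with one camera, comparing cameras is also comparing groups of centers, and the planned test cannot tell the two apart. The one comparison that could, camera against camera within a center, is not planned.

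The study's stated purpose is to inform later studies. A misattributed camera p-value could misdirect the choice of camera, or the decision to pool cameras, in those studies. In principle a center difference could also mask a real camera difference, but that direction has not been quantified.

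**Working it through.** **What there is to reproduce.** The SAP gives no alpha, power or expected difference for the camera test, and the sample size of about 60 rests on historical experience. No stated figure can be reproduced, so the question was examined by simulating the planned test with no true camera effect.

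**Inputs from the documents**

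- About 60 patients and up to 10 centers: 60 / 10 = 6 patients per center.
- Up to 15 standard-of-care specimens per patient (Protocol 6.3).
- Breslow-Day test on one table per camera (SAP 7.10.3.4).

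**Assumed inputs**

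- Alpha 0.05; 2 or 3 camera systems; one camera per center.
- 8 tumor and 7 benign specimens per patient, with specimens independent within center.
- Mean sensitivity 85% and specificity 70%.
- Normal center effects on the logit scale.

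**What the SDs mean.** The 95% range across centers is expit(logit(p) ± 1.96 × SD), with logit(0.85) = 1.735 and logit(0.70) = 0.847.

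| SD | Sensitivity | Specificity |
|---|---|---|
| 0.3 (±0.588) | 76-91% | 56-81% |
| 0.5 (±0.980) | 68-94% | 47-86% |

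**Rejection rate at 0.05, no true camera effect, cameras nested in centers** (ranges cover 2 and 3 cameras)

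| Type of center difference | SD 0 | SD 0.3 | SD 0.5 |
|---|---|---|---|
| Sensitivity and specificity vary independently | about 5% | 13-16% | 22-34% |
| Reading threshold only (one rises, the other falls, odds ratio fixed) | about 5% | about 5% | about 5-6% |

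**Second set of assumptions.** This used 10 tumor and 5 normal specimens per patient, sensitivity 80% and specificity 70%.

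- Sensitivity and specificity moving together: 15-21% at SD 0.25 and 35-52% at SD 0.5.
- Specificity alone varying: 16-20% at SD 0.5.
- Threshold only: 4.9-6.3% over SD 0.25 to 0.5.

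**Is it confounding or test calibration?** Under the second set, with two cameras each used for half the patients in every center, the rate was 3.5-5.2% at SDs of 0.5 and 1.0. The inflation above therefore comes from the link between camera and center. With partial overlap, under the main assumptions and two cameras, the rate was about 12-16% at SD 0.5. This figure depends on how much overlap is assumed and falls toward nominal as the cameras become balanced within centers.

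**Why threshold differences escape the p-value.** The diagnostic odds ratio is [Se/(1−Se)] × [Sp/(1−Sp)].

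- Se 0.70, Sp 0.85: (0.70/0.30) × (0.85/0.15) = 2.333 × 5.667 = 13.2.
- Se 0.90, Sp 0.595: (0.90/0.10) × (0.595/0.405) = 9 × 1.469 = 13.2.

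The odds ratios agree and Breslow-Day gives p = 1.0. The by-camera table would nevertheless show sensitivity 70% against 90% and specificity 85% against 59.5%.

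**The case against.** The strongest objection is that the premise is not in the documents. Camera system is recorded per patient, nothing says that a site has only one, and if cameras are well mixed within centers the false-positive rate is near nominal. This stands. A reader might infer that cameras are in fact tied to sites, and the documents do not support that. They are equally silent on any arrangement that would prevent it, and the plan has no step to find out.

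A reader might also infer that any surgeon or center difference will produce a camera p-value. That is too strong. A surgeon who calls fluorescence more readily mainly shifts the threshold, and Breslow-Day largely misses such a shift. The by-camera sensitivity and specificity in the same summary do not miss it.

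Thirdly, SAP 7.6 might be read as prohibiting a within-center comparison. It states only that none is planned. Protocol 9 allows further analyses, and SAP 7.10.3.5 allows post hoc covariates without closing the list. But that list is optional and does not name center or surgeon, and SAP 7.6 does say that center differences stay out of the analyses.

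Finally, the consequence is limited. The objective is exploratory, the study is not powered for testing, and no decision rule hangs on this p-value. That also stands and sets the weight of the point.

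**Conclusion.** The point holds conditionally. As written, SAP 7.10.3.4 reads a difference in odds ratios between cameras as a camera effect, and nothing in the plan separates camera from center or surgeon. If cameras are nested in centers and sensitivity and specificity vary independently between centers, a nominal 5% test rejects in about 13-16% of trials at SD 0.3 and 22-34% at SD 0.5. Limited overlap reduces this to about 12-16% at SD 0.5 with two cameras. If centers differ only in reading threshold, the p-value stays near 5% and only the descriptive by-camera figures mislead.

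These rates rest on assumed center SDs, baseline accuracy, specimen mix, equal center sizes and 60 evaluable patients. The documents supply none of these, and the 60 already allows for non-evaluable patients. Specimens were taken as independent within a center. Patient-level correlation alone, with no center effect, gave 8.3-9.4% at a patient SD of 0.5 under the second set of assumptions, which is a separate source of inflation.

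The primary endpoint and the overall accuracy estimates are unaffected. Weight: low.

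**What to change.** Amend SAP 7.10.3.4, with a matching exception in SAP 7.6:

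1. Tabulate camera system by center before any comparison.
2. Where enough centers used more than one camera, compare cameras within center, with center as a stratum or a random effect.
3. Otherwise, present the by-camera table without a p-value and label differences 'camera or center'.

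The cost is SAP wording and one cross-tabulation. Camera is already recorded, and center is known in any multicenter trial. There are two downsides. At about 6 patients per center the within-center strata will be sparse, so step 2 may give imprecise results. If cameras do not overlap within centers, the p-value has to be dropped, because stratifying by center cannot then separate the two effects.
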